10.3 POPULATIONS FOR ANALYSES

The main analyses (i.e., for primary endpoints), unless otherwise noted, will be performed on an intent-to-treat basis that include all randomized participants.

The main analysis of smoking abstinence will be performed on a complete-case basis, using all available outcome data in the modeling with treatment condition as randomized. Sensitivity analyses will be performed 1) on an intent-to-treat basis imputing missing as smoking and 2) using multiple imputation with chained equations to handle missing data. This analytic strategy is consistent with expert recommendations and statistical practice,⁴⁰ because the assumption of missing = smoking may be biased in favor of the group with lower attrition.⁴¹⁻⁴³

10.4 STATISTICAL ANALYSES

10.4.1 GENERAL APPROACH

The main analyses will be conducted on an intent-to-treat basis using all randomized participants. Adjusted regression models described below will adjust for a range of potential confounders, including gender, age, race/ethnicity, baseline smoking intensity, and years smoked. Multiple imputation using chained equations (MICE) for arbitrary missingness patterns^{44, 45} will be used for sensitivity analyses. In further analyses, we will estimate adjusted regression models on a per-protocol basis.

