5 STUDY DESIGN

5.1 OVERALL DESIGN

The pilot trial will be a two-arm randomized trial of 500 adult users of the Smoke Free app. We will set a quota to include at least 100 individuals age ≥ 50 years old to explore differential program effects by age. The goal of the pilot trial is to assess whether a video game increased engagement with the app, relative to a version of the app without the game. The primary outcome is the number of app opens per participant.

Our primary hypothesis is that the app with the game will increase a user’s engagement, as objectively measured by number of unique app sessions and average minutes of app usage per session. Our secondary hypotheses are that the app with the game will increase retention, early efficacy, and program adherence (use of core app features).

During the study period, participants will be randomized in a 1:1 ratio to the core version of the Smoke Free app plus the game module or to the same core version of the Smoke Free app without the game module (a two-arm trial). Assessors of the follow-up cotinine test to assess smoking status will be blinded; other research personnel will not be. Individuals will be invited to participate in the pilot trial in the initial onboarding screens within the Smoke Free smartphone app, with a link to a screening questionnaire and consent form in Qualtrics. We will recruit individuals age ≥ 18 years old living in the US who smoke at least 1 cigarette per day and have downloaded the Smoke Free app, plan to quit smoking within 7 days, are able to speak, read, and write in English, and are willing to provide a saliva test sample. Participation will last until 8 weeks (56 days) after the person’s selected quit day.

Participants will be asked to complete a baseline questionnaire in Qualtrics after consenting to participate in the study and a follow-up questionnaire in Qualtrics at the end of the 56-day period. Those reporting being smoke-free in the follow-up questionnaire will be mailed a salivary cotinine test kit to upload photos of the test results that biochemically verify smoking status.

The main engagement analyses will be conducted on an intent-to-treat basis using all randomized participants. Regression models will adjust for a range of potential confounders, including gender, age, race/ethnicity, cigarettes per day at baseline, and years smoked.

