10.2 SAMPLE SIZE DETERMINATION

The pilot trial sample size is powered to detect meaningful differences in our primary outcome of number of times the app is opened.

As this is a pilot study, a main objective will be to provide empirical data for effect size estimation for a future full-scale RCT. Thus, our sample size is based on budget and feasible accrual during the study timeline.

With two parallel groups, the sample size calculation was conducted for one of our primary outcomes, a continuous measure of the number of times the Smoke Free app was opened through Day 56 of the study period.

We anticipate that a sample size of 500, with an assumed 70% retention, toward the high end for app-based smoking cessation trials,^{19, 39} will yield a final sample size of 350 at the final assessment. We further anticipate a mean number of app opens of 30.0 per participant and a standard deviation of 45.0 in the core app, based on recent data from users of Smoke Free. A sample size of 350 participants will allow us to detect a between-group difference in app opens, one of the primary outcomes, of 13.5 at 80% power ($\alpha=0.05$).

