10.4.2 ANALYSIS OF THE PRIMARY ENDPOINT(S)

Our key hypothesis is that the gamified app improves engagement measured by number of app opens through Day 56 following the participant's quit date. To test this, we will compare the mean number of app opens by arm, using an adjusted linear model with an indicator for treatment arm.

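### Does the app-opens analysis need a stated rule for missing covariates before it can include everyone randomized?

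*Combined protocol and SAP*

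**What the plan says.** The population is stated three times. Section 5.1: "The main engagement analyses will be conducted on an intent-to-treat basis using all randomized participants". Section 10.3 says that analyses of the primary endpoints "will be performed on an intent-to-treat basis that include all randomized participants", and Section 10.4.1 repeats the commitment.

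Section 10.4.2 compares mean app opens by arm "using an adjusted linear model with an indicator for treatment arm". Section 10.4.1 names the covariates: "Adjusted regression models described below will adjust for a range of potential confounders, including gender, age, race/ethnicity, baseline smoking intensity, and years smoked". Of multiple imputation by chained equations it says only that it "will be used for sensitivity analyses". The complete-case rule in Sections 10.3 and 10.4.3 is confined to smoking abstinence.

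Age and cigarettes per day are known before allocation, because they are the randomization strata (Section 7.3). For gender, race/ethnicity and years smoked, the readable text names no instrument. The screening questionnaire comes before randomization. The baseline questionnaire is e-mailed after consent and may be returned up to Day 7 (Sections 1.3 and 9.1). The contents of neither are listed, and the schema in Section 1.2 is not shown in the copy reviewed.

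Section 10.2 assumes 70% retention of 500, which "will yield a final sample size of 350 at the final assessment". It continues: "A sample size of 350 participants will allow us to detect a between-group difference in app opens", namely 13.5 opens at 80% power.

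**The concern.** A linear model cannot use a record with an empty covariate, and standard software drops it without comment. If three of the five covariates came from a questionnaire answered after allocation, a default fit would exclude non-responders. That would break the all-randomized commitment and condition the primary comparison on behaviour that the assigned app version might influence. Only the cotinine assessors are blinded (Section 7.3), and Section 5.1 hypothesizes that the game raises retention.

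The plan is visibly more careful about missing data for abstinence. There it warns that counting missing as smoking "may be biased in favor of the group with lower attrition" and sets out two sensitivity analyses. The primary endpoint has no equivalent rule. The power statement, resting on 350, can then be read as a sign that 150 people are expected to drop out of this analysis too. At stake would be a biased arm difference and a type I error rate other than 5%.

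**Working it through.** **1. The plan's own figure.** Inputs from Section 10.2: SD 45, alpha 0.05, power 80%, N = 350. The alternative in Section 10.1 is non-directional, so the test is taken as two-sided; equal SDs in the arms are assumed. Allocation is 1:1 (Section 7.3).

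Detectable difference = (1.960 + 0.842) × 45 × √(4/N).

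- N = 350 (500 × 0.70): 13.48 opens. Power for 13.5 is 80.1%. The stated figure reproduces.
- N = 500: 11.28 opens. Power for 13.5 is 91.8%.

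**2. Precision if non-completers were dropped.** The documents give no completion rate for the baseline questionnaire. Assumed rates of 80%, 90% and 95% leave N = 400, 450 and 475, with power for 13.5 of 85.1%, 88.9% and 90.5%. Power stays at or above the stated level unless more than 30% of participants are lost.

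**3. Bias, for illustration.** Only the mean of 30 and SD of 45 come from the plan. Assume that there is no true effect, that covariates come from the baseline questionnaire, that non-completers are deleted and average m opens in both arms, and that SD 45 holds among completers. With completion c, completers average m + (30 − m)/c, so

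bias (game minus control) = (30 − m) × (1/c_game − 1/c_control), and SE = 45 × √(1/n_control + 1/n_game), with n = 250c per arm.

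| Completion, control / game | m | Bias (opens) | SE | Two-sided type I error | False claims for the game |
|---|---|---|---|---|---|
| 85% / 90% | 5 | −1.63 | 4.30 | 6.7% | 1.0% |
| 85% / 90% | 20 | −0.65 | 4.30 | 5.3% | 1.7% |
| 80% / 90% | 5 | −3.47 | 4.37 | 12.5% | 0.3% |
| 80% / 90% | 20 | −1.39 | 4.37 | 6.2% | 1.1% |

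First row: (30 − 5) × (1/0.90 − 1/0.85) = 25 × (−0.0654) = −1.63.

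If the game raises completion, the error runs against the game: false claims for it fall below the nominal 2.5%. If the game lowers completion by the same gap, the tails swap and false claims for it become 3.5% to 5.7% (5 points) or 5.0% to 12.2% (10 points). Equal completion by the same kinds of participants gives zero bias.

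**4. What the text supports.** The bias needs three conditions together.

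- *Covariates taken from the post-randomization questionnaire:* not stated. If they are asked at screening, missingness cannot depend on arm and only precision is affected.
- *Completion that differs by arm:* not documented. The retention hypothesis concerns staying in the program, not returning a form by Day 7. The attrition warning concerns follow-up abstinence. Section 6.5 schedules reminders and pays $20 for the baseline survey, both of which tend to reduce missingness.
- *Deletion of non-completers:* contrary to the commitment made in three sections.

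**The case for a change.** The strongest case for a change is that the main model leaves an analyst a choice on the primary endpoint. Imputation, a missing category and deletion are all open, and deletion is what software does by default. Settling the choice before data are seen would take a sentence or two and reuse imputation work already planned. Because app opens are recorded passively, loss at the final questionnaire does not by itself remove the outcome, so the 350 in Section 10.2 is unexplained.

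The factual part stands: the readable text has no rule for a missing covariate in this model and names no source for three covariates. But deletion is not an equal option for an analyst told three times to include everyone randomized. Section 10.4.1 places multiple imputation in the general approach, so on its natural reading the sensitivity analysis covers app opens as well. A main fit that lost people would differ from it in the number analysed, and the loss would be seen. Section 4 also defines the endpoint through mean opens by group, which needs no covariates.

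The point about 350 is separate, since that number comes from retention and not from missing covariates. It works as a margin. Section 8.2 has the app stop collecting study data on withdrawal, so some later opens can be missing and complete data on 500 is a best case. Section 10.2 also says that the size rests on budget and feasible accrual, so a restated detectable difference would alter no decision.

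**Conclusion.** The concern describes a real omission of detail, of the kind that analysts fill sensibly, and not a wrong rule or figure. The governing instruction is clear, complete-case analysis is reserved for abstinence, and the means of keeping everyone in the model is already in the plan. The power statement is correct and errs on the safe side: 13.5 opens at 350, against 11.3 at 500 if no app data are lost.

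The biases of 0.65 to 3.47 opens, and type I error rates of 5.3% to 12.5%, rest on assumed completion rates, an assumed gap between arms, assumed use among non-completers and deletion that the plan does not adopt. They show what could happen under those inputs and are not evidence of a defect. The conclusion would change if the three covariates proved to come only from the baseline questionnaire, completion differed materially by arm, and the analysts deleted incomplete records. The documents establish none of these, so no change is called for.

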10.4.2 ANALYSIS OF THE PRIMARY ENDPOINT(S)

Our key hypothesis is that the gamified app improves engagement measured by number of app opens through Day 56 following the participant's quit date. To test this, we will compare the mean number of app opens by arm, using an adjusted linear model with an indicator for treatment arm.

10.4.3 ANALYSIS OF THE SECONDARY ENDPOINT(S)

To measure retention, we will compare the proportion who complete the program by arm using an adjusted logistic model.

To measure early efficacy, we will use adjusted logistic models to compare abstinence by treatment condition for 7- and 30-day point-prevalence. Analyses for smoking abstinence will be performed on a complete-case basis, using all available data in the modeling with treatment condition as randomized. Sensitivity analyses will be performed 1) on an intent-to-treat basis imputing missing as smoking and 2) using multiple imputation with chained equations to handle missing data. This analytic strategy is consistent with expert recommendations and statistical practice,⁴⁰ because the assumption of missing = smoking may be biased in favor of the group with lower attrition.⁴¹⁻⁴³

Post-hoc analyses will also explore the self-reported reasons un-subscribers opt out and predictors thereof.

10.4.4 SAFETY ANALYSES

N/A

10.4.5 BASELINE DESCRIPTIVE STATISTICS

We will calculate descriptive statistics for demographic and smoking variables and compare means by study condition to check equivalence. To assess engagement, retention, and abstinence, we will carefully tally and summarize these measures and test for demographic and smoking-related variables such as age that may be related to them.

10.4.6 PLANNED INTERIM ANALYSES

No interim analyses are planned.

10.4.7 SUB-GROUP ANALYSES

We will test for effect modification of engagement by examining interactions between treatment condition and selected factors, including age, race/ethnicity, household income, smoking intensity, years smoked, dual/poly tobacco use, prior video game experience, impulsivity, and sensation seeking.

10.4.8 TABULATION OF INDIVIDUAL PARTICIPANT DATA

Individual participant data will not be listed by measure or time point.

10.4.9 EXPLORATORY ANALYSES

N/A

11 SUPPORTING DOCUMENTATION AND OPERATIONAL CONSIDERATIONS

11.1 REGULATORY, ETHICAL, AND STUDY OVERSIGHT CONSIDERATIONS

11.1.1 INFORMED CONSENT PROCESS

11.1.1.1 CONSENT/ASSENT AND OTHER INFORMATIONAL DOCUMENTS PROVIDED TO PARTICIPANTS

Consent forms describing in detail the study intervention, study procedures, and risks will be sent by e-mail to the participant, and documentation of (signed) informed consent will be completed prior to starting the study intervention.

11.1.1.2 CONSENT PROCEDURES AND DOCUMENTATION

Only English speakers above 18 years of age may participate in this study. Participants will receive an online screen with the informed consent form as soon as they qualify for the study based on the eligibility screening questionnaire. Participants will be required to check a box at the end of the informed consent form to indicate "Yes, I agree to participate in the study."

11.1.2 STUDY DISCONTINUATION AND CLOSURE

This study may be temporarily suspended or prematurely terminated if there is sufficient reasonable cause. Written notification, documenting the reason for study suspension or termination, will be provided by the suspending or terminating party to study participants, investigator, funding agency, and regulatory authorities. If the study is prematurely terminated or suspended, the Principal Investigator (PI) will promptly inform study participants, the Institutional Review Board (IRB), and sponsor/funding agency and will provide the reason(s) for the termination or suspension. Study participants will be contacted, as applicable, and be informed of changes to study visit schedule.

Circumstances that may warrant termination or suspension include, but are not limited to:

- Determination of unexpected, significant, or unacceptable risk to participants

- Insufficient compliance of study staff to the protocol (ie, significant protocol violations)
- Data that are not sufficiently complete and/or evaluable
- Determination that the primary endpoint has been met
- Determination of futility

The study may resume once concerns about safety, protocol compliance, and data quality are addressed, and satisfy the funding agency, sponsor, IRB, Food and Drug Administration (FDA), or other relevant regulatory or oversight bodies.

11.1.3 CONFIDENTIALITY AND PRIVACY

During this pilot trial, data will be collected via Qualtrics, the Smoke Free app, and photographs (to verify saliva cotinine test results).

Confidentiality will be maintained via study identification (ID) codes assigned to individual participants and removal of identifying information from all transcripts, survey questionnaires, or other data records.

Only research team members and staff associated with UCSF's IRB will have access to the study data.

Participant confidentiality is strictly held in trust by the investigators and study staff.

The study protocol, documentation, data, and all other information generated will be held in strict confidence. No information concerning the study or the data will be released to any unauthorized third party without prior written approval of the PI.

23 Limited, which operates the Smoke Free app, will collect de-identified information on study participants' app usage for the 56-63 day study period. The file will be shared via Box with its TLS 1.2 encryption and linked to study data using the de-identified study identifier.

11.1.4 FUTURE USE OF STORED SPECIMENS AND DATA

N/A

11.1.6 SAFETY OVERSIGHT

There is no DSMB in place for this project because it is a pilot study that it poses minimal risk to participants as determined by the UCSF IRB.

11.1.7 CLINICAL MONITORING

N/A

11.1.8 QUALITY ASSURANCE AND QUALITY CONTROL

Quality control (QC) procedures will be implemented as follows:

Source documents and the electronic data --- Data will be initially captured on source documents (see **Section 11.1.9, Data Handling and Record Keeping**) and will ultimately be entered into the study database. To ensure accuracy investigators will compare a representative sample of source data against the database, targeting key data points in that review.

Intervention Fidelity — Consistent delivery of the study interventions will be monitored throughout the intervention phase of the study by the Smoke Free team. Procedures for ensuring fidelity of intervention delivery are described in **Section 7.2.1, Interventionist Training and Tracking**.

Protocol Deviations — The study team will review protocol deviations on an ongoing basis and will implement corrective actions when the quantity or nature of deviations are deemed to be at a level of concern.

In addition, all study personnel will be appropriately trained in his/her position's duties with appropriate Human Subjects Research training. They will be provided with full information about the study such as background and significance, specific aims, milestones, study designs, procedures, and analytic plans. All team members will be encouraged to view themselves as crucial team members encouraged to comment, ask questions, and make suggestions to ensure the highest study quality; robust and rigorous data will be gathered and handled according to protocol.

The PI will ensure that this study is conducted in full conformity with the principles set forth in The Belmont Report: Ethical Principles and Guidelines for the Protection of Human Subjects of Research, as drafted by the US National Commission for the Protection of Human Subjects of Biomedical and Behavioral Research (April 18, 1979) and codified in 45 CFR Part 46 and/or the ICH E6.

Should independent monitoring become necessary, the PI will provide direct access to all trial related sites, source data/documents, and reports for the purpose of monitoring and auditing by the sponsor/funding agency, and inspection by local and regulatory authorities.

11.1.9 DATA HANDLING AND RECORD KEEPING

11.1.9.1 DATA COLLECTION AND MANAGEMENT RESPONSIBILITIES

During this pilot trial, data will be collected via Qualtrics, the Smoke Free app, and photographs (to verify cotinine test status).

Confidentiality will be maintained via study identification (ID) codes assigned to individual participants and removal of identifying information from all transcripts, survey questionnaires, or other data records.

Only bona-fide research team members and staff associated with UCSF's IRB will have access to the study data.

The study protocol, documentation, data, and all other information generated will be held in strict confidence. No information concerning the study or the data will be released to any unauthorized third party without prior written approval of the PI.

23 Limited, which operates the Smoke Free app, will collect de-identified information on study participants' app usage patterns. The file will be shared via Box with its TLS 1.2 encryption and linked to study data using the de-identified study identifier.

11.1.9.2 STUDY RECORDS RETENTION

Study documents will be retained for a minimum of 2 years after the last approval of a marketing application in an International Council on Harmonisation (ICH) region and until there are no pending or contemplated marketing applications in an ICH region or until at least 2 years have elapsed since the formal discontinuation of clinical development of the study intervention. These documents should be retained for a longer period, however, if required by local regulations. No records will be destroyed without the written consent of the sponsor/funding agency, if applicable. It is the responsibility of the sponsor/funding agency to inform the investigator when these documents no longer need to be retained.

11.1.10 PROTOCOL DEVIATIONS

This protocol defines a protocol deviation as any noncompliance with the clinical trial protocol, International Council on Harmonisation Good Clinical Practice (ICH GCP), or Manual of Procedures (MOP) requirements. The noncompliance may be either on the part of the participant, the investigators, or Smoke Free employees. As a result of deviations, corrective actions will be developed by the site and implemented promptly.

These practices are consistent with ICH GCP:

- Section 4.5 Compliance with Protocol, subsections 4.5.1, 4.5.2, and 4.5.3
- Section 5.1 Quality Assurance and Quality Control, subsection 5.1.1
- Section 5.20 Noncompliance, subsections 5.20.1, and 5.20.2.

It will be the responsibility of the PI to use continuous vigilance to identify and report deviations within 10 working days of identification of the protocol deviation, or within 10 working days of the scheduled protocol-required activity. All deviations will be addressed in study source documents, reported to NIH National Cancer Institute and NIH National Institute on Aging Program Official and to UCSF. Protocol deviations will be sent to the reviewing Institutional Review Board (IRB) per their policies. The site investigator will be responsible for knowing and adhering to the reviewing IRB requirements.

Major (reportable) protocol violations are any unapproved changes in the research study design and/or procedures that are within the investigator's control and not in accordance with the IRB-approved protocol that may affect the participant's rights, safety or well-being, or the completeness, accuracy and reliability of the study data. We **will report** all major violations to the HRPP/IRB using the Protocol Violation/Incident Report Form in iRIS and also to the NIH as described above.

Minor (non-reportable) protocol violations (also known as protocol deviations) are any unapproved changes in the research study design and/or procedures that are within the investigator's control and not in accordance with the IRB-approved protocol that **do not have a major impact** on either the participant's rights, safety or well-being, or the completeness, accuracy and reliability of the study data. We will **not report** minor protocol violations to the UCSF IRB/HRPP, but we will document them in the study files and report them to the NIH if applicable.

